2.3 ANALYSIS POPULATIONS

2.3.1 Enrolled population

The enrolled population is defined as patients who were randomized in the double-blind period and enrolled in open-label period analyzed according to the treatment group allocated by randomization in double-blind period (ie, placebo/teriflunomide versus teriflunomide/teriflunomide).

2.3.2 Efficacy population

The efficacy population is defined as all patients enrolled and were treated with at least 1 dose of teriflunomide in the open-label treatment period analyzed according to the treatment group allocated by randomization in the double-blind period (ie, placebo/teriflunomide versus teriflunomide/teriflunomide).

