2.1.3.1 Primary efficacy endpoint(s)

The primary efficacy endpoint is the time to first clinical relapse after randomization up to end of double-blind treatment period, which is not directly applicable for the open-label treatment period since Relapse Adjudication Panel (RAP) of the double-blind period was not continued into the open-label period. Refer to the SAP for the double-blind period of the study.

However, time to first clinical relapse after randomization in double-blind period up to the end of the open-label treatment period will be performed on relapses with objective signs on the Examining Neurologist's examination (which is the basis for RAP confirming relapses) as a primary efficacy endpoint for analysis period from randomization to the end of the open-label period.

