2.1.3.3 Additional efficacy endpoints

The following endpoints, which have not been planned in the protocol for the double-blind period, are added as relevant for efficacy analysis of the open-label period.

- Annualized relapse rate (ARR) since the enrollment into the open-label period up to the exit of the open-label treatment period.
- Time to sustained disability progression (using EDSS) since randomization in double-blind period up to the end of open-label treatment period.

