2.4.4 Analyses of efficacy endpoints

All the following efficacy analysis will be conducted on efficacy population, according to the treatment group allocated by randomization in the double-blind period (ie, placebo/teriflunomide versus teriflunomide/teriflunomide). Baseline values of the double-blind period will be used as the baseline in the efficacy analysis for the open-label CSR, unless otherwise noted.

Analyses of efficacy endpoints of the open-period period are of exploratory intent in principle. Long-term treatment effects and the 95% confidence intervals, where applicable, will be assessed since the randomization date in the double-blind period throughout the last visit of the open-label period of the study; unless otherwise noted. P-values will be provided if applicable. No confirmative conclusion should be drawn based on p-value because of exploratory nature of open-label period analysis.

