2.4.4.1 Analysis of primary efficacy endpoint

Clinical relapses are defined as new or recurrent neurological symptoms not associated with fever or infection, lasting at least 24 hours, and accompanied by new objective neurological findings upon examination by the Examining Neurologist and documented by the Functional System Scores (FSS). New or recurrent symptoms that occur less than 30 days following the onset of a relapse are considered part of the same relapse.

Note that the process of confirmation of clinical relapse is different between the double-blind period and the open-label period. Confirmation in the double-blind period involves the Relapse Adjudication Panel (RAP), whereas confirmation in the open-label period is done by the investigative center. However, some analyses will combine confirmed relapses from both treatment periods, as the criteria used in the two processes are similar.

The first clinical confirmed relapse occurring from randomization in the double-blind period (including relapses during the PK run-in (8 weeks) phase) to the end of the open-label period will be included for analysis. Treatment effect as measured by the hazard ratio and its associated 95% confidence interval will be estimated using a Cox proportional-hazards model with robust variance estimation (1). Cox model will include factors for treatment group, region, pubertal status, age, and number of relapses in the year prior to randomization. The duration of time to the event will be included in the modeling to offset the lengths of individual observations. Kaplan-Meier estimates of probability of clinical relapse at Week 24, 48, 72, 96, 120, 144, 168 and 192 will be estimated. The complementary log-log transformation will be used to construct 95% confidence intervals. A Kaplan-Meier survival curve from randomization in double-blind period to the end of open-label period will be presented. A stratified log-rank test with time to first clinical relapse as the dependent variable, treatment group as a test variable, region (definition of the regions are provided in [Section 2.5.5](#)), and pubertal status as covariates will be provided as supportive.

Censoring rule

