The minimum EDSS increase used to define disability progression is referred to as “minimum increase” in the following text. The initial EDSS increase that meets this “minimum increase” criterion is referred to as “the onset”. An EDSS measurement at or after 24 weeks following the onset is necessary to confirm the initial increase and is referred to as “24-week EDSS confirmation”. All EDSS measurements (with or without relapse) will be used to determine the onset of a disability progression. However, for the purpose of confirmation, only EDSS measured more than 30 days after the onset of a confirmed relapse will be used to avoid a confirmation caused by a temporary relapse. In order to confirm that the EDSS increase is persistent for at least 24 weeks, the following conditions have to be satisfied: (1) The 24-week EDSS confirmation needs to maintain at least the minimum increase; (2) all EDSS measurements between the onset and the 24-week EDSS confirmation need to maintain at least the minimum increase. Once a disability progression is confirmed, time to disability progression is defined as “date of onset - date of randomization (in the double-blind period) + 1”. If a patient has no disability progression on or before last during treatment EDSS evaluation, then the patient is considered as disability progression free until the date of last during treatment EDSS evaluation. The last during treatment EDSS evaluation is defined as last measurement during treatment period (measurement at last scheduled visit for patients who complete the treatment, or measurement at the close-out visit for patients who discontinue the treatment).

If a patient dies for any reason without a 24-week EDSS confirmation, the disability progression will be considered as confirmed with the date of the onset as the date of progression unless any EDSS measured within the 24 weeks did not maintain the minimum increase. Death due to MS (EDSS=10) will be counted as confirmed progression. The progression date is the date of death if there is no prior qualifying EDSS increase and it is the date of the first qualifying EDSS increase if there is such an EDSS increase prior to the death. All the derivation will be based on the exact EDSS evaluation date. Since the actual visit may have been ± 7 days from the scheduled visit, a -7 days window will be used to define the period of 24 weeks.

Censoring rules

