- If a patient has no EDSS increase that meets the criteria for progression before treatment discontinuation/completion, then the patient will be considered as free of progression till the date of last during-treatment EDSS evaluation.
- If a patient has an EDSS increase that meets the criteria for progression before treatment discontinuation, all available EDSS assessments obtained during the follow-up visits will be used to serve the purpose of progression confirmation. The patient will be considered as having disability progression if the first increase during treatment period is confirmed for at least 24 weeks during the follow-up visits. If the EDSS from the follow-up visit(s) does not confirm a sustained increase or despite all possible attempts, no confirmatory EDSS assessment is obtained after withdrawal, the patient will be considered as free of disability progression until the date of last during treatment EDSS evaluation.
- If a patient has an EDSS increase that meets the criteria for progression and completes the treatment period before the progression can be confirmed, then the patient will be considered as free of progression till the date of last during-treatment EDSS evaluation.
- In rare cases, if a patient had a delayed EDSS scheduled during the open-label period but performed during the optional extension period due to the Covid-19 pandemic, then this assessment will still be considered as during-treatment EDSS evaluation. The delayed EDSS result will be considered in the sustained disability progression determination process in the open-label analysis.
- In rare cases, if a patient had a delayed EDSS scheduled during the open-label period but performed after treatment discontinuation due to the Covid-19 pandemic, then the delayed EDSS result will be used for progression confirmation purpose only.

The hazard ratio and 95%CI for teriflunomide/teriflunomide versus placebo/teriflunomide will be estimated using Cox regression model with treatment group, region and baseline pubertal status as covariates, offset by the lengths of individual observations.

The Kaplan-Meier method will be used to estimate median time (if possible) to disability progression sustained for at least 24 weeks and cumulative disability progression rates specific to each treatment group. Kaplan-Meier graphs will be generated; quartiles and point probabilities will be calculated. Interval estimates will be calculated using 95% point wise confidence intervals.

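### Relapse and disability progression are timed from randomization and compared by randomized arm, but only in patients who later took an open-label dose, so both hazard ratios are conditional on open-label entry

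*SAP*

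**What the plan says.** **Analysis set.** SAP 2.3.2 defines the efficacy population as "all patients enrolled and were treated with at least 1 dose of teriflunomide in the open-label treatment period analyzed according to the treatment group" given at randomization. SAP 2.4.4 states "All the following efficacy analysis will be conducted on efficacy population", and Appendix B lists no other set for either endpoint.

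**Time origin and contrast.** SAP 2.4.4 also says "Long-term treatment effects and the 95% confidence intervals, where applicable, will be assessed since the randomization date in the double-blind period".
- Relapse: SAP 2.1.3.1 adopts it "as a primary efficacy endpoint for analysis period from randomization to the end of the open-label period", and SAP 2.4.4.1 takes "The first clinical confirmed relapse occurring from randomization in the double-blind period", with a Cox hazard ratio by arm.
- Progression: SAP 2.1.3.3 adds "Time to sustained disability progression (using EDSS) since randomization in double-blind period up to the end of open-label treatment period". SAP 2.4.4.3.2 computes the time as "date of onset - date of randomization (in the double-blind period) + 1" and adds: "The hazard ratio and 95%CI for teriflunomide/teriflunomide versus placebo/teriflunomide will be estimated using Cox regression model".

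**Who can enter open label.** Under Protocol 5.1 and 8.1, entry is an option after a relapse confirmed by the Relapse Adjudication Panel once the 8-week run-in is over, after high MRI activity, or on completing 96 weeks. Protocol 9.8.6 requires fresh consent.

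**Who is left out.** Patients who stop double-blind drug for other reasons, and eligible patients who decline, are not in the efficacy population. Protocol 10.3.2 plans roughly 12-weekly follow-up of early stoppers, including EDSS and relapse reporting, to the end of the double-blind period.

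**The concern.** Membership of the analysis set is decided after the clock starts, and one route into the set is the endpoint event itself. A patient who relapses after Week 8 can qualify at once. A relapse-free patient who stops early is removed together with all of the event-free time already observed. A patient who relapses and declines open label is removed together with the event.

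The comparison keeps the randomized labels but no longer covers the randomized groups. If early stopping, or uptake after relapse, differs by arm, the hazard ratio can leave 1.00 with no drug effect. The SAP calls the result a treatment effect since randomization and does not say that it applies only to open-label entrants. The relapse censoring rule in SAP 2.4.4.1 speaks only of discontinuation or completion in the open-label period, so it has no provision for a patient who never entered.

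**Working it through.** **Inputs from SAP 1.3.** Two-year placebo relapse 60%; hazard ratio 0.5; 110 teriflunomide and 55 placebo; 20% two-year discontinuation for reasons other than relapse.

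**Step 1: reproduce the plan's figures.** Placebo hazard = -ln(0.4)/2 = 0.4581 per year. Half of this is 0.2291, and the teriflunomide two-year risk is 1 - exp(-2 x 0.2291) = 36.8%. All three match. An exponential log-rank sample size with pooled variance and dropout hazard -ln(0.8)/2 = 0.1116 gives 167.5 patients against the planned 165, and 79.5% power at 165.

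**Step 2: share excluded.** Ignoring the run-in rule, the share that drops out before relapse and before Week 96 is d/(d+h) x [1 - exp(-(d+h) x 96/52.18)].
- Placebo: 0.1116/0.5697 x [1 - exp(-1.048)] = 12.7%.
- Teriflunomide: 0.1116/0.3407 x [1 - exp(-0.627)] = 15.3%.

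A relapse in Weeks 0 to 8 counts as an event but does not open entry. With that rule, simulation gives 13.6% and 15.8%. This is 0.136 x 55 + 0.158 x 110, or about 25 of 165 patients, carrying about 1 of 90 relapses.

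**Step 3: effect on the 192-week relapse hazard ratio.** Simulation used 4,000,000 patients for the plan inputs and 2,500,000 for each assumed case. Relapse and dropout are exponential, every eligible patient enters unless stated, and both arms have the teriflunomide hazard after Week 96. There is no open-label dropout and no switching for high MRI activity. In the no-effect case both arms have hazard 0.4581 throughout. The comparison set counts every on-treatment relapse and censors event-free never-entrants at dropout or Week 96.

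| Case | All randomized and treated | Open-label entrants only |
|---|---|---|
| Plan inputs, effect present | 0.602 | 0.608 |
| Plan inputs, no effect | 1.00 | 1.00 |
| Assumed dropout 25% placebo, 10% teriflunomide: effect / no effect | 0.60 / 1.00 | 0.58 / 0.96 |
| Assumed dropout 10% placebo, 25% teriflunomide: effect / no effect | 0.60 / 1.00 | 0.64 / 1.04 |
| Assumed uptake after relapse 95% placebo, 90% teriflunomide: effect / no effect | 0.60 / 1.00 | 0.59 / 0.98 |
| Assumed uptake after relapse 90% placebo, 95% teriflunomide: effect / no effect | 0.60 / 1.00 | 0.62 / 1.02 |

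The standard error of the log hazard ratio at 165 patients is about 0.216. On unrounded output the plan-input shift is about 0.04 of one standard error; the rounded values give ln(0.608/0.602)/0.216 = 0.046. The dropout imbalances shift it by up to 0.25 and the uptake imbalances by up to 0.17. The documents give only the overall 20%; the splits by arm and the uptake rates are assumptions. A separate run of 600,000 patients per case agrees: 0.594 to 0.603 on plan inputs, and 0.957 or 1.051 in place of 1.00 under the two dropout splits.

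**Step 4: Week 96 relapse-free proportion.** If it is timed from randomization, the plan inputs move it from 43.1% to 40.6% on placebo and from 65.6% to 63.4% on teriflunomide.

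**Step 5: progression.** The documents give no progression rate in this population, so no shift can be calculated.

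**The case against.** The strongest reply is that the shift is trivial on the plan's own inputs, and that every larger figure needs an imbalance between arms that no passage predicts. That stands. Protocol 5.1 keeps patients, investigators and the study team blinded, which makes arm-specific uptake less likely. It does not rule out arm-specific dropout, for example through tolerability.

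Second, the arms are labelled as treatment sequences, the SAP declares the analyses exploratory (2.4.4 and 2.4.4.4), and the disposition table in 2.2 shows randomized, discontinued and enrolled counts by arm. This softens the risk of misreading but does not remove it. Those percentages use open-label enrolled patients as the denominator and are not split by prior relapse, and exploratory status does not tell the reader which population a hazard ratio describes.

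Third, the protocol's double-blind ITT analysis already uses the on-treatment relapses of patients who never entered, and a sensitivity analysis in Protocol 11.4.4.1 adds relapses after discontinuation. That is true for relapse to Week 96. It does not cover progression, which SAP 2.1.3.3 says was not planned in the protocol for the double-blind period.

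A reader might also carry the point to the T2-lesion-free and disease-free proportions. The documents do not support that. SAP 2.1.3.2 ties these endpoints to the open-label period, at the open-label MRI visits of Table 2, and the windows in 2.5.3 count days from first dose within each period. Open-label timing is at least as natural a reading. Relapse timed from open-label enrollment and the annualized relapse rate start at open-label enrollment, so they do not have this mismatch.

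**Conclusion.** The point holds for two endpoints: time to first clinical relapse and time to sustained disability progression, both from randomization. Their hazard ratios are conditional on open-label entry, and the SAP does not say so.

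For relapse, the expected shift is below 0.01 on the plan's inputs, and a null stays null. A shift of 0.02 to 0.04 needs an assumed 15-point dropout imbalance. These figures also assume that dropout is unrelated to relapse risk. For progression the size is unknown.

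A reader might infer that the restriction favours teriflunomide or weakens the trial's main result. Neither follows. The direction depends on which arm loses more patients, and the double-blind primary analysis uses the ITT population of Protocol 11.3.1.1 and is untouched. This is an inexpensive improvement to exploratory analyses.

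**What to change.** In SAP 2.3.2, 2.4.4 and Appendix B, analyse these two endpoints in all randomized and treated patients (the protocol ITT population).
- Count every qualifying on-treatment event, including those of patients who never entered open label.
- Censor event-free never-entrants at the last double-blind dose for relapse and at the last during-treatment EDSS for progression. Let follow-up EDSS confirm an on-treatment onset, as SAP 2.4.4.3.2 already does.
- Keep the open-label efficacy population as a supplementary analysis, labelled as conditional on open-label entry.
- In SAP 2.4.4.2.2, state the time origin of the relapse-free proportions. If it is randomization, use the same population.
- In SAP 2.2, report never-entrants by arm and by prior relapse, with randomized and treated patients as the denominator.

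The cost is SAP wording, one extra disposition split and a re-run of two exploratory analyses, plus the relapse-free proportions if they are timed from randomization. No new data collection is needed.

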2.3.3 Safety population

The safety population is defined as all patients enrolled in the open-label treatment period and received any dose of teriflunomide in the open-label period. It will be used for the safety analyses in the open-label period.

The safety analyses will be conducted according to the treatment patients actually received in the double-blind and open-label period (placebo/teriflunomide versus teriflunomide/teriflunomide) as well as the overall treatment group.

2.3.4 Pharmacokinetic population

The PK population is a subset of the safety population containing patients who have at least one PK sample taken in the open-label period. Patients will be analyzed in the treatment group corresponding to the treatment actually received as defined for the safety population.

2.4 STATISTICAL METHODS

2.4.1 Demographics and baseline characteristics

All demographics and baseline characteristics parameters will be summarized on the enrolled population analyzed in the treatment group to which they were allocated to in the double-blind and open-label period (placebo/teriflunomide versus teriflunomide/teriflunomide) as well as the overall treatment group. Analyses for the safety population will be included in the appendices if the size of the safety population is different (>10%) from the size of that in the efficacy population for any treatment group.

Continuous data will be summarized using the number of available data, mean, standard deviation (SD), median, minimum, and maximum for any treatment group. Categorical and ordinal data will be summarized using the number and percentage of patients with non-missing data (unless otherwise noted) in any treatment group.

Parameters described in [Section 2.1.1](#) will be summarized by treatment group and overall treatment groups using descriptive statistics. P-values or statistics tests on demographic and baseline characteristic data will not be calculated.

Medical and surgical history

Medical and surgical history will be summarized by primary SOC and HLT for each treatment group. The table will be sorted by SOC internationally agreed order and decreasing frequency of HLT based on the overall incidence in the overall treatment group.

No specific description of the safety parameters will be provided at baseline. If relevant, the baseline values will be described along with each safety analysis.

No specific description of the efficacy parameters will be provided at baseline. If relevant, the baseline values will be described along with each efficacy analysis.

2.4.2 Prior or concomitant medications

The prior or concomitant medications will be presented for the enrolled population. Analyses for the safety population will be included in the appendices if the size of the safety population is different (>10%) from the size of that in the efficacy population for any treatment group.

Medications will be summarized by placebo/teriflunomide, teriflunomide/teriflunomide and overall treatment groups according to the WHO-DD dictionary, considering the first digit of the Anatomic Therapeutic Chemical (ATC) class (anatomic category) and the first 3 digits of the ATC class (therapeutic category). All ATC codes corresponding to a medication will be summarized, and patients will be counted once in each ATC category (anatomic or therapeutic) linked to the medication. Therefore patients may be counted several times for the same medication.

The table for prior medications will be sorted by decreasing frequency of ATC followed by all other therapeutic classes based on the incidence in the overall treatment groups. In case of equal frequency regarding ATCs (anatomic or therapeutic categories), alphabetical order will be used.

The tables for concomitant and follow-up medications will be sorted by decreasing frequency of ATC followed by all other therapeutic classes based on the incidence in the overall treatment group. In case of equal frequency regarding ATCs, alphabetical order will be used.

In addition, prior MS medication, the inducers and systemic corticosteroid treatment for MS relapse will be analyzed by number and percentage of confirmed relapse requiring steroid treatment.

